4.2.10 Exposure to Study Drug

Duration of exposure to study drug will be calculated as follows from the date of last dosing minus the first day of dosing + 1. The duration of exposure calculation will not take into account interruptions in therapy/missed doses. Duration of exposure to study drug will be reported in months. Patients will also be assigned to a duration of exposure category (< 1 month, 1 to < 3 months, 3 to < 6 months, 6 to < 12 months, ≥12 months) based on their exposure. Additionally actual number of days dosed will be calculated taking into account interruptions and missed doses.

Cumulative dose taken (mg) will be the sum of all doses taken by a patient taking into account any interruptions/missed doses, dose reductions or dose increases as recorded in the eCRF

$$\sum_{j=1}^j dose (mg)_j * (end\ date_j - start\ date_j + 1)$$

Dose intensity (mg/day) is calculated as cumulative dose taken (mg)/duration of exposure (days).

QMD Ref: CCI	Governing QMD: CCI
Confidentiality Statement	
CCI	
REF: CCI	Page 12 of 45

CCI			
CCI		Sponsor:	Theseus Pharmaceuticals, Inc.
CCI		Protocol Number:	THE630-21-101
STATISTICAL ANALYSIS PLAN. PHASE 2-3-4			

Relative dose intensity is calculated as 100* (dose intensity/expected dose intensity). Expected dose is based on assigned dose level and duration of exposure not adjusted for prescribed interruptions, dose reduction or increases.

4.2.11 Compliance

Treatment compliance for Cycle 1 will be calculated as follows: ([cumulative] amount of treatment actually taken [mg] during Cycle 1)/Total [cumulative] amount of treatment that should have been taken [mg] during Cycle 1 x 100. Total (cumulative) amount taken for cycle 1, similar to calculation in Section 6.2.10 limiting to Cycle 1. Total (cumulative) amount of treatment that should have been taken (mg) during Cycle 1 will be calculated for each dose level prescribed within Cycle 1*(end date of that dose level -start date of dose level+1) and summed across dosing records within Cycle 1 for a given patient. Patients will also be categorized by Cycle 1 compliance based on the following compliance levels (<50%, 50 to <75%, 75 to <90%, ≥ 90%).

4.2.12 Body Mass Index (BMI)

BMI at screening will be derived based on screening height and weight.

BMI = weight (kg) divided by height (m) squared (unit=kg/m²).

4.2.13 Safety Endpoints

4.2.13.1 Electrocardiogram (ECG) Data

Triplicate ECGs should be taken on Cycle 1, Day 1 (pre-dose and 8 hrs post-dose) and Day 15 (pre-dose and following hrs post-dose: 1, 2, 4, 8); otherwise, single ECGs are required at specific time points per protocol schedule of events.

For triplicate ECG data recorded on continuous scales, the mean value rounded to the integer will be presented. For overall interpretation if more than one value is recorded, the most severe (worst case) of the respective readings will be taken.

4.2.13.2 Dose Limiting Toxicities (DLT)

DLTs during Phase 1 (dose escalation phase) are defined as any treatment-emergent adverse event (AE) that meets the following criteria within the first 28 days of treatment (e.g, occurring during Cycle 1) and for which the relationship to THE-630 cannot be ruled out:

- Non-hematologic toxicities
 - Any ≥ Grade 3 non-hematologic toxicity, with the exception of:

QMD Ref: CCI		Governing QMD: CCI	
Confidentiality Statement			
CCI			

CCI			
CCI	Sponsor:		Theseus Pharmaceuticals, Inc.
	Protocol Number:		THE630-21-101
STATISTICAL ANALYSIS PLAN. PHASE 2-3-4			

- Self-limiting or medically controllable toxicities (e.g., nausea, fatigue, electrolyte disturbances) lasting ≤ 3 days
 - Grade 3 vomiting or diarrhea lasting ≤ 3 days
 - Grade 3 elevations of creatine kinase (CK) that are asymptomatic, i.e., not accompanied by muscle pain or worsening renal function or other signs of rhabdomyolysis or cardiac muscle damage (such as abnormal CK-MB, Troponin) and recovered to \leq Grade 1 or baseline in <72 hours
 - Grade 3 hypertension that recovers to Grade 2 or below within 5 days
 - Alopecia
- Hematologic toxicities
 - Febrile neutropenia (fever, $>101^{\circ}\text{F}$ [$>38.3^{\circ}\text{C}$]; ANC $<0.5 \times 109/\text{L}$)
 - Prolonged Grade 4 neutropenia (≥ 7 days)
 - Neutropenic infection: \geq Grade 3 neutropenia with \geq Grade 3 infection
 - Thrombocytopenia \geq Grade 3 with bleeding or Grade 4 without bleeding lasting ≥ 7 days
 - Missed $\geq 25\%$ of planned doses of THE-630 (in the aggregate, not necessarily consecutive) over 28 days due to AEs for which the relationship to THE-630 cannot be ruled out in the first cycle [note the treatment-related AE(s) included should not have met other DLT criteria]

DLTs will be reported as AEs and identified as a DLT in the database.

4.2.13.3 *Unscheduled Visits*

Only scheduled post-baseline laboratory, vital signs, ECHO/MUGA and ECG values will be tabulated by visit. Certain summaries may have any time, post-baseline/worst post-baseline/minimum post-baseline/maximum post-baseline which would include post-baseline scheduled/repeat/ unscheduled assessments. All post-baseline assessments will be listed in the relevant appendices to the CSR.

4.2.14 **Efficacy endpoints**

QMD Ref: CCI	Governing QMD: CCI
Confidentiality Statement	
CCI	

CCI		Sponsor: Theseus Pharmaceuticals, Inc.	
CCI		Protocol Number: THE630-21-101	
STATISTICAL ANALYSIS PLAN. PHASE 2-3-4			

4.2.14.1 Best Overall Response (BOR), Confirmed

BOR is defined as the best response achieved at any time point on the study where response refers to the overall response at a given time point (e.g., overall visit response; (derived; see [Appendix 1](#))) according to the following hierarchy:

- Complete Response (CR),
- Partial Response (PR),
- Stable disease (SD)
- Progressive disease (PD)
- Not Evaluable (NE)

per modified RECIST version 1.1 for patients with GIST.

CR or PR responses must be confirmed by repeat imaging at no less than 4 weeks after the date of the initial response (See [Appendix 1](#)). To be assigned SD, patient must have met the SD criteria once after first dose at a minimum of 6 weeks. It should be noted that patients with no measurable disease at baseline should have overall visit response(s) of Non-CR/Non-PD. In these cases, for analysis purposes, BOR will be set to NE. Additionally, if a patient does not have any post-baseline overall visit response assessments, then the patient will be assigned BOR of NE.

4.2.14.2 Confirmed Objective Response Rate (ORR)

Confirmed ORR is defined as the proportion of the patients who were confirmed to have achieved CR or PR per modified RECIST version 1.1 for patients with GIST (confirmed ≥ 4 weeks after initial response with a subsequent scan) after initiation of study drug. Patients with no measurable disease at baseline or no evaluable post-baseline response assessment (e.g., RECIST) will be considered non-responders.

4.2.14.3 Clinical Benefit Rate (CBR) at 16 Weeks

CBR at 16 weeks is defined as the proportion of patients remaining on study who have not met criteria for progressive disease (PD) on or prior to the 16-week assessment (i.e., patients with an objective response or stable disease (SD) lasting 4 cycles from the start of treatment (defined as at least 109 days from start of treatment). Patients with no tumor assessments (e.g., scans) for Week 16 and later timepoints would not be counted as having clinical benefit.

QMD Ref: CCI	Governing QMD: CCI
Confidentiality Statement	
CCI	
REF: CCI	Page 15 of 45

CCI			
CCI	Sponsor:		Theseus Pharmaceuticals, Inc.
	Protocol Number:		THE630-21-101
STATISTICAL ANALYSIS PLAN. PHASE 2-3-4			

4.2.14.4 Disease Control Rate (DCR)

DCR is defined as the proportion of patients who have achieved confirmed BOR of CR, PR, or SD (in the case of SD, measurements must have met the SD criteria at least 6 weeks after the initiation of study drug).

4.2.14.5 Best Percent change from baseline in sum of the longest diameter of target lesions

The percentage change in the sum of longest diameter for the target lesions by visit will be calculated. Best percent change in the sum of the longest diameter (SLD) of target lesions will be identified. This is defined as the biggest percent reduction from baseline or in the scenario where patient does not have any reduction then no change or smallest increase.

That said post-baseline visits where the longest diameter of one or more of the identified target lesions(s) were not measured and the target lesion response for said visit is NE will be excluded for purposes of analysis ([Appendix 1](#)).

4.2.14.6 Duration of Follow-up

Duration of follow-up is defined as time (months) from first dose until death, lost to follow-up (ltfu) or withdraw from study, whichever is earliest.

Duration of follow-up (months)= (earliest of date of death/ltfu/withdraw from study- date of first dose + 1)/30.4375.

4.3 Conventions

All data listings, summaries, figures, and statistical analyses will be generated using SAS version 9.3 or higher¹.

Dose Escalation (Phase 1) [DE]:

DE or DE cohort refers subjects participating in the Phase 1 dose escalation part of this study. Cohort for DE phase refers to dose level.

Summaries will be presented by dose escalation phase cohorts (dose levels) and overall.

3 mg QD (N=XX)	<Dose 2 level> (N=XX)	<Dose 3 level> (N=XX)	<Dose 4 level> (N=XX)	<Dose X level> (N=XX)	All Patients (N=XXX)
-------------------	--------------------------	--------------------------	--------------------------	--------------------------	-------------------------

QMD Ref: CCI	Governing QMD: CCI
Confidentiality Statement	
CCI	

CCI			
CCI		Sponsor:	Theseus Pharmaceuticals, Inc.
		Protocol Number:	THE630-21-101
STATISTICAL ANALYSIS PLAN. PHASE 2-3-4			

Listings will be sorted in the following order: Cohort number, patient (if applicable, backfill patients should be listed after non-backfill patients), parameter, and visit unless otherwise stated. All data will be listed.

Continuous variables will be summarized by the number of non-missing observations, mean, median, standard deviation, and minimum and maximum.

Categorical variables will be summarized by presenting the frequency and percent. Percentages will be based on the number of non-missing observations unless otherwise specified. For each variable, all categories will be shown. Zero frequencies (but not the percent) within a category will be presented.

4.3.1 Decimal Places

Decimal places for derived data described in section 4.2 will be determined by the scale of measurement unless otherwise stated. No decimal places will be displayed if the smallest calculated value is ≥ 100 ; 1 decimal place will be displayed when the smallest value is within the interval (10, 100), with 10 being inclusive; 2 decimal places will be displayed when the smallest value is within (1, 10), with 1 being inclusive; and so on for even smaller scales of measurement.

Derived data where it is known in advance the result will be an integer for example day, month, year, number of days and total scores (for rating scales) will be presented with zero decimal places.

Means, medians and percentiles will be displayed to one more decimal place than the data, dispersion statistics (e.g. standard deviation) will have two more decimal places, and the minimum and maximum will be displayed to the same number of decimal places as reported in the raw data. Percentages will be displayed with one decimal place.

4.4 Patient Disposition

Patient disposition will be summarized as follows:

- The number of patients, who are in the Screened Set, Enrolled Set, Full Analysis Set and DLT-Evaluable Set will be summarized by cohort and overall.
- The number of patients who failed screening and the reasons for failure will be tabulated for the Screened Set
- The number and percentage of patients who discontinued study drug along with the reason for discontinuing drug and those who discontinued the study along with the reason for discontinuing the study will be tabulated by cohort and overall for the Full Analysis Set.

QMD Ref: CCI	Governing QMD: CCI
Confidentiality Statement	
CCI	

CCI		Sponsor: Theseus Pharmaceuticals, Inc.	
CCI		Protocol Number: THE630-21-101	
STATISTICAL ANALYSIS PLAN. PHASE 2-3-4			

- Duration of follow-up will be summarized by cohort and overall for the Full Analysis Set.

4.5 Protocol Deviations

Number (percent) of patients with Major Deviations by deviation category will be presented by cohort and overall for Full Analysis Set.

4.6 Baseline Comparability

The comparability of cohorts with respect to patient demographics and baseline characteristics will be assessed in a descriptive manner, but no formal statistical testing will be performed.

The following baseline demographic variables will be summarized by cohort and overall for the Full Analysis Set using standard continuous or categorical variable summaries: Age at informed consent (years), gender, ethnicity, race, height, weight and BMI.

4.7 Medical History

Medical history conditions (prior and on-going) and previous surgical procedures reported at screening will be presented together for Full Analysis Set. Terms will be coded by Medical Dictionary of Regulated Activities (MedDRA) primary system organ class (SOC) and preferred term.

4.8 Baseline Characteristics

Reported mutation status history (e.g, presence of any kit mutation, type of kit Exon mutation, presence of any PDGRA mutation, type of PDGRFA Exon Mutation, Kit and PDGRFA wild-type status) will be summarized by cohort and overall for Full Analysis Set.

Details regarding GIST history (initial diagnosis: time from first diagnosis of GIST to first dose of study drug (years), stage at initial diagnosis, current stage, primary tumor location, histology, any prior surgery related to GIST, any prior radiation therapy related to GIST and any Systemic Anticancer Therapy (SACT) related to GIST; current stage and location of sites of disease at screening) will be summarized by cohort and overall for the Full Analysis Set.

QMD Ref: CCI	Governing QMD: CCI
Confidentiality Statement	
CCI	
REF: CCI	Page 18 of 45

CCI			
CCI		Sponsor:	Theseus Pharmaceuticals, Inc.
		Protocol Number:	THE630-21-101
STATISTICAL ANALYSIS PLAN. PHASE 2-3-4			

The ECOG performance status scale measures a patient’s level of daily functioning (scale ranges from grades 0-5). Descriptive statistics of baseline ECOG score will be presented by cohort and overall.

Details regarding SACT related to GIST (any prior SACT, number of prior therapies, number of prior regimens, number of prior TKIs, type of SACT) will be summarized by cohort and overall for Full Analysis Set.

Details regarding prior surgery and radiation therapy will not be summarized or listed.

4.9 Prior and Concomitant Medications

Data will not be summarized or listed.

4.10 Non-Pharmacological Procedures

Data will not be summarized or listed.

4.11 Exposure to Study Drug

Extent of exposure (number of days of exposure to study), actual number of days dosed, the cumulative amount of administered treatment, dose intensity, and relative dose intensity will be summarized by cohort and overall for Full Analysis Set. Additionally, the number (percent) of patients that had an interruption lasting 3 days or more, duration of longest interruption for those subjects with an interruption lasting at least 3 days, number (percent) of patients that had an interruption due to an AE, number (percent) of patients that had a dose reduction due to an AE or dose increase will also be summarized by cohort and overall.

4.12 Treatment Compliance

Compliance for Cycle 1 will be summarized by cohort and overall for the Full Analysis Set.

4.13 Efficacy Analyses

No statistical comparisons between cohorts are planned for this study. All efficacy analyses will be conducted on the full analysis set unless otherwise stated.

4.13.1 Efficacy Analysis

- ORR

QMD Ref: CCI	Governing QMD: CCI
Confidentiality Statement	
CCI	

CCI			
CCI	Sponsor:		Theseus Pharmaceuticals, Inc.
	Protocol Number:		THE630-21-101
STATISTICAL ANALYSIS PLAN. PHASE 2-3-4			

ORR (confirmed) will be summarized by each cohort and overall along with corresponding exact binomial 2-sided 95% CI.

Descriptive summaries will be provided for the confirmed best overall response (BOR) and time to response (confirmed) by cohort and overall.

A waterfall plot of the best percentage change in the target lesion sum of longest diameters from baseline will be produced by cohort. Additionally, swimmer's plots of the duration of treatment overlaid with overall timepoint response will be produced.

- DCR and CBR

DCR and CBR at 16 weeks will be summarized by each cohort and overall along with corresponding exact binomial 2-sided 95% CI.

4.14 Pharmacokinetic Analyses

Pharmacokinetic analyses will be analyzed and reported in a separate report.

4.15 Safety Analyses

The safety analyses will be presented by the treatment received for the Full Analysis Set.

4.15.1 Adverse Events

A treatment-emergent adverse event (TEAE) is defined as:

- Any AE that has an onset on or after the first dose of study drug and before last dose + 30 days
- Any pre-existing AE or medical history finding that has worsened in severity on or after the first dose of study drug

A post-treatment AE is Any AE that has an onset greater than 30 days after last dose of study drug.

If an AE has missing relationship it is assumed to be related to the study drug for analysis purposes.

If a toxicity grade is missing, then the toxicity grade will be reported as missing.

The following tables will be presented for AEs:

- Overall incidence and number of TEAE, TEAEs \geq Grade 3, Treatment-Related TEAEs, Treatment-Related TEAEs \geq Grade 3, Serious Treatment Emergent Adverse Events (Treatment-Emergent SAEs), Serious Treatment-Related TEAEs (Treatment Emergent,

QMD Ref: CCI	Governing QMD: CCI
Confidentiality Statement	
CCI	

CCI		Sponsor: Theseus Pharmaceuticals, Inc.	
CCI		Protocol Number: THE630-21-101	
STATISTICAL ANALYSIS PLAN. PHASE 2-3-4			

Treatment-Related SAEs), TEAEs leading to Study Drug discontinuation, TEAEs leading to interruption of study drug, TEAEs leading to dose reduction of study drug and Fatal TEAEs.

- TEAEs by system organ class and preferred term, incidence and number of events.
- Treatment related TEAE by system organ class and preferred term, incidence and number of events.
- TEAEs \geq Grade 3 by system organ class and preferred term, incidence and number of events.
- Treatment-related TEAEs \geq Grade 3 by system organ class and preferred term, incidence and number of events.
- Serious TEAE by system organ class and preferred term, incidence and number of events.
- Serious Treatment related TEAE by system organ class and preferred term, incidence and number of events.
- TEAEs Leading to Discontinuation of Study Drug b system organ class and preferred term
- TEAEs Leading to Interruption of Study Drug by system organ class and preferred term, incidence and number of events.
- TEAEs Leading to dose reduction of Study Drug by system organ class and preferred term, incidence and number of events.
- TEAE by system organ class, preferred term and maximum toxicity, incidence.
- Treatment-Related TEAE by system organ class, preferred term and maximum toxicity, incidence.
- Fatal TEAEs by system organ class and preferred term, incidence
- Post-Treatment Adverse Events by system organ class and preferred term, incidence and number of events.
- Adverse Events, Dose Limiting Toxicities during Cycle 1 By Preferred Term and maximum toxicity, incidence (Phase 1 only; DLT-Evaluable Analysis Set)
- Listing of Serious TEAEs
- Listing of Fatal TEAEs
- Listing of All Deaths
- Listing of DLTs

All AEs will be listed.

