### **8.2 Definition of Adverse Events, Period of Observation, Recording of Adverse Events**

An Adverse Event (AE) is any untoward medical occurrence in a clinical investigation patient administered a pharmaceutical product and that does not necessarily have a causal relationship with this treatment. An AE can therefore be any unfavorable and unintended sign (including an abnormal laboratory finding), symptom, or disease temporally associated with the use of a medicinal (investigational) product, whether or not related to the medicinal (investigational) product ([ICH E2A, 1995](#)). All AEs should be captured on the AE eCRF.

All AEs are collected from the time of informed consent through at least 30 days after the last dose of study drug. Beyond 30 days after the last dose, ongoing AEs for which relationship to THE-630 cannot be ruled out, and all ongoing serious adverse events (SAEs) should be followed at least every 4 weeks until they resolve to baseline (or to NCI CTCAE v5.0 grade  $\leq 1$ ), stabilize, or are considered to be chronic/irreversible. In addition, SAEs observed by the investigator or reported by the patient that occur after 30 days after the last dose of study drug through the end of the survival follow-up period should be reported if there is a reasonable possibility that the event may have been caused by THE-630, even if the investigator becomes aware of such events after the end of the survival follow-up period.

Once a patient is deemed a screen failure, AE collection is no longer required.

All AEs are to be recorded on the appropriate AE pages in the eCRF and in source documents. Where possible, a diagnosis, rather than a list of symptoms, should be recorded. If a diagnosis has not been made, then each symptom should be listed individually. In addition to untoward AEs, unexpected benefits outside the study drug indication should also be captured on the AE eCRF.

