#### **8.2.1 Severity Categorization**

AE severity should be graded per the NCI CTCAE v5.0 definitions listed in [Appendix 3](#).

The severity of AEs must be recorded over the course of the event, including the start and stop dates. An event that changes with worsening severity should be captured as a new event. Worsening of pre-treatment events, after initiation of study drug, must be recorded as new AEs (for example, if a patient experiences mild intermittent dyspepsia prior to dosing of study drug, but the dyspepsia becomes severe and more frequent after first dose of study drug has been administered, a new AE of severe dyspepsia [with the appropriate date of onset] is recorded on the appropriate eCRF).

If the AE is not defined in the CTCAE, the Investigator will determine the severity of the AE based on the following definitions:

- *Mild (grade 1)*: The AE is noticeable to the patient but does not interfere with routine activity
- *Moderate (grade 2)*: The AE interferes with routine activity but responds to symptomatic therapy or rest
- *Severe (grade 3)*: The AE significantly limits the patient's ability to perform routine activities despite symptomatic therapy
- *Life-Threatening (grade 4)*: The patient is at immediate risk of death
- *Death (grade 5)*: The patient dies as a direct result of the complication or condition induced by the AE

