4.2.3 Duration / Study Day / Time

Study day will be calculated as the number of days from first dose of study drug.

- date of event – date of first dose of study drug + 1, for events on or after first dose
- date of event – date of first dose of study drug, for events before first dose

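### SAP 4.15.1 puts an adverse event that starts exactly 30 days after last dose in neither the treatment-emergent nor the post-treatment class

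*SAP*

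**What the plan says.** SAP 4.15.1 gives the treatment-emergent (TEAE) definition two limbs. The first is by onset: "Any AE that has an onset on or after the first dose of study drug and before last dose + 30 days". The second is by worsening: "Any pre-existing AE or medical history finding that has worsened in severity on or after the first dose of study drug". The complementary class is then defined: "A post-treatment AE is Any AE that has an onset greater than 30 days after last dose of study drug".

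Four other places bear on how these rules work:

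- **Day count.** SAP 4.2.3 says "Study day will be calculated as the number of days from first dose of study drug". It gives no convention for counting days after last dose.
- **Collection.** Protocol 8.2 says "All AEs are collected from the time of informed consent through at least 30 days after the last dose of study drug". This is a collection rule; the protocol sets no TEAE window.
- **Worsening.** Protocol 8.2.1 says "Worsening of pre-treatment events, after initiation of study drug, must be recorded as new AEs", each with its own onset date.
- **Presentation.** SAP 4.3 says "Summaries will be presented by dose escalation phase cohorts (dose levels) and overall".

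The AE incidence tables in SAP 4.15.1 and Section 9 are each limited to TEAEs or a subset of them, to post-treatment events, or to Cycle 1 DLTs.

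**The concern.** The two classes should meet at day 30 after last dose so that every event from first dose onward falls in exactly one. As written they do not meet. One limit stops short of day 30 and the other starts after it, so a new-onset event on that day is collected, belongs to no class, and is counted in no incidence table. The protocol's dedicated safety contact is nominally 30 days (±7) after last dose (Protocol 6.4.1), so the unclassified day is the last day of the required collection period.

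The worsening limb errs the other way. With no end date, it keeps late worsening treatment-emergent indefinitely, while the onset date of the newly recorded event also makes it post-treatment.

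At stake is the accuracy of the tables that describe the Phase 1 safety profile, which is the primary endpoint. Section 9 marks the AE tables for independent programming. Two programmers could resolve the wording differently, or both could code the gap faithfully.

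**Working it through.** Let d = onset date minus last-dose date, in days.

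**Rules as written**

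- TEAE, new onset: onset on or after first dose, and d < 30.
- TEAE, worsening: on or after first dose, no upper limit on d.
- Post-treatment: d > 30.

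| d | New onset, as written | Worsening recorded as a new AE, as written | Either kind, revised rules |
|---|---|---|---|
| 29 | TEAE | TEAE | TEAE |
| 30 | neither | TEAE | TEAE |
| 31 | post-treatment | both | post-treatment |

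The revised rules use d ≤ 30 on both TEAE limbs and leave post-treatment at d > 30. The new-onset results, as written and with the inclusive limit, were checked by date arithmetic for treatment lasting 1, 28 and 90 days. They were the same each time: as written only d = 30 was unclassified, and the inclusive limit left no gap and no overlap.

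**Can the DLT table catch d = 30?** DLTs must fall "within the first 28 days of treatment". The earliest study day for d = 30 arises when first and last dose are both on day 1: 30 + 1 = day 31, which is later than 28. So no, and for the same reason DLT and MTD results cannot be affected.

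**Why the day count must be stated.** If last dose were counted as day 1 in the post-treatment rule, d = 30 would become day 31 and be post-treatment. The gap would then close without any edit. But making the TEAE limit inclusive under that count would put d = 30 in both classes. SAP 4.2.3 adds one day only when counting from first dose, so the text does not support that reading, but nothing rules it out explicitly.

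**Where the overlap would show.** A serious, related worsening at d ≥ 31 qualifies for Table 14.3.1.7 (serious treatment-related TEAEs) and for Table 14.3.1.14 (post-treatment related SAEs).

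**Weight of one affected patient.** Enrollment stopped at 32 (SAP Section 1), and Protocol Table 3 gives 3 to 6 patients per escalation cohort.

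- All Patients column: 1/32 = 3.1 points, if all 32 were dosed.
- Dose level with 3 patients: 1/3 = 33.3 points.
- Dose level with 6 patients: 1/6 = 16.7 points, and less where backfill adds patients.

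Each figure applies only if the patient has no other event of the same term already counted.

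**The case against.** The strongest reply is that this is a drafting slip. The two sentences are plainly meant as complements, and the on-treatment window for QTcF in SAP 4.15.6 runs up to last dose plus 30 days, most naturally read as including that day. This is a fair account of intent, and it supports the inclusive limit proposed here. It does not remove the gap, because the written rule is what gets programmed.

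Second, other outputs would still show some day-30 events. The death listing (14.3.2.2) has no window, the SAE listing (14.3.2.3) is not limited to TEAEs by its title, and abnormal laboratory values are listed throughout the study. That stands. What is lost is the incidence count, and a non-serious day-30 event that is not a laboratory abnormality may have no output at all. SAP 4.15.1 says that all AEs are listed, but version 3.0 drops every listing not referenced as a table, and heading 16.2.7 is empty.

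Third, under Section 9 an event at d = 31 that is not a related SAE also reaches no AE incidence table, unless it comes in through the worsening limb. That is true, but such an event at least has a class. The day-30 event has none, even when it is a related SAE.

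Fourth, once worsening is recorded as a new AE, a reader might class it by onset alone, making it post-treatment only. The SAP does not say so, and on its literal text both definitions are met. The two tables are separate and no sum of them is planned, so the harm is inconsistency, not an inflated total.

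Finally, the percentage-point figures give the weight of any one patient in a small group, not an estimate of how often the defect occurs. That is correct, and they should be read that way.

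**Conclusion.** The concern holds and is minor. Followed exactly, SAP 4.15.1 leaves a new-onset event at d = 30 unclassified, and the unbounded worsening limb makes late worsening both treatment-emergent and post-treatment.

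The gap is one calendar day per patient; the overlap can arise on any day from d = 31. The documents do not support an estimate of how many events either fault affects. AE output is descriptive, and DLT and MTD conclusions are untouched.

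The conclusion rests on counting days after last dose as a plain date difference. It also rests on treating worsening as a new AE with its own onset date, as Protocol 8.2.1 requires.

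**What to change.** In SAP 4.15.1:

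1. Make the upper limit of the first TEAE limb inclusive, so that onset on the date of last dose plus 30 days counts as treatment-emergent. Leave the post-treatment limit at more than 30 days.
2. State that, for both definitions, days after last dose are onset date minus last-dose date.
3. State how worsening of a pre-existing condition after day 30 is classed. Giving the second limb the same end date would make later worsening post-treatment only.

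Three editorial items can be settled in the same edit, by aligning the 4.15.1 text with Section 9:

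- The text describes a table of all post-treatment AEs, while 14.3.1.14 covers only related SAEs.
- The text says all AEs are listed, while 16.2.7 is empty.
- The text names a listing of serious TEAEs, while 14.3.2.3 is titled as an SAE listing.

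The cost is one inclusive limit, one sentence, one clause and three text edits. No new table, listing or data is needed. Because version 3.0 is signed, the change needs a further version or a documented clarification.

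### The worsening limb of the TEAE definition has no end date, so a pre-dose condition that worsens more than 30 days after last dose is both a TEAE and a post-treatment AE

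*SAP*

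**What the plan says.** SAP 4.15.1 sets three rules.

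- New-onset limb of the TEAE definition: "Any AE that has an onset on or after the first dose of study drug and before last dose + 30 days".
- Worsening limb of the TEAE definition: "Any pre-existing AE or medical history finding that has worsened in severity on or after the first dose of study drug".
- Post-treatment class: "A post-treatment AE is Any AE that has an onset greater than 30 days after last dose of study drug".

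Protocol 8.2.1 governs how a worsening enters the database: "Worsening of pre-treatment events, after initiation of study drug, must be recorded as new AEs". Its worked example gives the record a separate date: "a new AE of severe dyspepsia [with the appropriate date of onset] is recorded on the appropriate eCRF".

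Protocol 8.2 sets the collection period: "All AEs are collected from the time of informed consent through at least 30 days after the last dose of study drug". After that, ongoing AEs possibly related to THE-630 are still followed, and "all ongoing serious adverse events (SAEs) should be followed at least every 4 weeks". New SAEs with a reasonable possibility of a drug cause are reportable to the end of survival follow-up. The 30-day contact has a window of 7 days either side (Schedule of Events, note 22).

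**The concern.** The new-onset limb has a start and an end. The worsening limb has only a start. The post-treatment class takes any AE with a late enough onset and does not exclude events that are already TEAEs. Neither document gives an order of precedence. A programmer who codes the three rules as written will set both flags on a late worsening of a pre-dose condition.

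The TEAE flag selects the records for nearly every AE table in the SAP: overall, Grade 3 or higher, serious, fatal, and those leading to interruption, reduction or discontinuation. Safety is the primary endpoint of Phase 1, so the definition should treat two events with the same onset day alike. As written, the class after day 30 depends on whether the condition existed before dosing.

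**Working it through.** The documents state no figure to reproduce. The check applies the three SAP 4.15.1 rules to an AE whose onset is *d* days after last dose, with the onset of a worsening dated as in Protocol 8.2.1.

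- New-onset limb: TEAE if *d* < 30.
- Worsening limb: TEAE for any *d* after first dose.
- Post-treatment: *d* > 30.

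| Onset, days after last dose | New-onset AE, as written | Worsening of pre-dose condition, as written | Either kind, after the fix |
|---|---|---|---|
| -10, 0, 29 | TEAE | TEAE | TEAE |
| 30 | neither class | TEAE | TEAE |
| 31, 37, 90 | post-treatment | TEAE and post-treatment | post-treatment |

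The overlap arises only for worsenings after day 30. A separate gap appears on day 30 itself: the new-onset limb stops before that day and the post-treatment class starts after it, so a new-onset AE on day 30 has no class.

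**Can such records exist?** There are three routes:

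1. The 30-day contact may fall on days 31 to 37 (30 + 7 = 37), and AE collection runs for at least 30 days.
2. SAEs are collected from consent. One that began before first dose and is still ongoing is followed after day 30 regardless of relationship, so its worsening can be recorded.
3. A late SAE judged possibly related may be a worsening of a pre-dose condition.

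**Size.** One record adds at most one patient to an incidence row.

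- All patients: 1/32 = 3.1 percentage points. The 32 is the number enrolled (SAP section 1). The Full Analysis Set counts those dosed, so this assumes all 32 were dosed.
- One dose level: 1/6 = 16.7 percentage points, assuming six patients. Escalation cohorts have three to six patients, plus any backfill.
- If the patient already counts in the row: 0.

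The error in an incidence row is therefore upwards or zero.

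**Display.** The text of SAP 4.15.1 lists a table of all post-treatment AEs. The table list in SAP section 9 has only Table 14.3.1.14, restricted to treatment-related SAEs. Under that list, a late worsening appears in both sets of tables only if it is a related SAE. Any other appears in the TEAE tables alone.

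**DLTs.** The earliest possible last dose is study day 1, and more than 30 days later is study day 32 or after. DLTs are confined to the first 28 days (SAP 4.2.13.2), so no affected record can be a DLT.

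**The case against.** The best counter-argument is that such records will hardly occur. Read with the phrase about first dose, pre-existing most naturally means present before dosing. The non-serious AEs followed after day 30 are those possibly related to THE-630, so they will nearly all have started on drug. If one of those worsens after day 30, its new record is not a worsening of a pre-dose condition and is post-treatment only. Medical history findings are not among the items followed after day 30. Protocol 8.2.1 says how a worsening is recorded, but does not lengthen the collection period. All of this stands, and it leaves only the three routes shown in the working. It does not cure the rule, which still gives two classes to any record that does arise.

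A reader might also infer more than the documents support:

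- That off-drug worsening would be attributed to THE-630. TEAE status is a matter of timing, and the SAP has separate treatment-related tables. New SAEs after day 30 are reportable only with a reasonable possibility of a drug cause, and expected progression of the disease is not an AE (Protocol 8.2.4).
- That the SAP declares the two classes mutually exclusive. It does not. The boundaries near day 30 suggest that intent, as does the ECG on-treatment window in SAP 4.15.6, which runs from first dose to last dose + 30 days, but this is inference.
- That every late record adds a patient to the TEAE tables. It does so only where the patient is not already counted in the row.

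**Conclusion.** The point holds as a definitional error with a small expected effect. A pre-dose condition that worsens more than 30 days after last dose is both a TEAE and a post-treatment AE, whereas a new-onset AE on the same day is post-treatment only.

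Few records are expected, and the figures of 3.1 and 16.7 points are maxima for a single row. The conclusion assumes that a worsening carries its own onset date, as Protocol 8.2.1 provides. If it were kept on the original pre-dose record, it would be a TEAE only. Dose-escalation decisions rest on Cycle 1 data and are not affected. This is a low-priority correction, worth making because the definition feeds nearly all the AE output and is cheap to repair.

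**What to change.** In SAP 4.15.1, give both TEAE limbs the same window: onset, or worsening, from first dose up to and including 30 days after last dose. This matches the on-treatment window already used for QTcF in SAP 4.15.6. Keep the post-treatment class as onset more than 30 days after last dose.

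Both limbs need to change. Capping only the worsening limb at day 30 inclusive would remove the overlap but leave a new-onset AE on day 30 without a class. With both limbs aligned, each AE from first dose onwards falls in exactly one class.

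The cost is one phrase in the SAP and one date condition in the program. If outputs already exist, list the AE records with onset on day 30 or later after last dose. That shows whether any table changes.
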